## **5.5 STUDY TREATMENT**

### **5.5.1 Upadacitinib Description**

Upadacitinib is an oral selective and reversible inhibitor of Janus kinase (JAK) 1, which blocks signaling of many inflammatory cytokines including interleukin (IL)-6, IL-2, IL-7, and IL-15. A growing body of evidence suggests that JAK inhibition is an effective therapy for the treatment of signs and symptoms of multiple immune-mediated inflammatory diseases in humans.

#### **5.5.1.1 Upadacitinib Dosing Schedule**

Subjects will be instructed to take Upadacitinib 15mg once daily starting at the baseline visit. Study drug should be taken approximately the same time each day. Study drug can be taken with or without food. If a subject forgets to take their dose at the regularly scheduled time they should take it immediately, unless it is within 10 hours of the next scheduled dose. If the next dose is expected within 10 hours than the forgotten dose

should be considered missed and the next dose should be taken at the regularly scheduled time.

#### **5.5.1.2 Upadacitinib Dispensing**

Subjects will return all unused upadacitinib tablets to the study site. Site personnel will keep a record of upadacitinib dispensed to and returned by each subject and note any missed doses.

#### **5.5.1.3 Upadacitinib Dosage Adjustments**

Upadacitinib will be dispensed and administered as 15mg QD at baseline. For subjects who do not achieve  $\leq$  2-point reduction in itch at week 8, upadacitinib dosage will be increased to 30mg QD. The investigator may reduce the dose to 15mg QD after week 16 per investigator discretion. If an SAE or an adverse event that is thought to be related to study drug and is not alleviated by symptomatic intervention, study drug will be discontinued. Subjects who permanently discontinue study drug under this protocol should receive standard care of prurigo nodularis treatment as prescribed by their physician.

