Study Endpoints	Primary Endpoint: Proportion of participants with improvement (reduction) in worst-itch numeric rating scale (WI-NRS) by $\geq 4$ from baseline to Week 12. [Time Frame: Baseline to Week 12 ]WI-NRS is a patient-reported outcome (PRO) comprised of a single item rated on a scale from 0 ("No itch") to 10 ("Worst imaginable itch). Secondary Endpoints: Proportion of patients with improvement in worst-itch numeric rating scale (WI-NRS) by $\geq 4$ from baseline to Week 24 IGA PN-S 0 or 1 at weeks 12 & 24 IGA PN-A 0 or 1 at week 12 & 24 Percent improvement of PN-S & PN-A at week 12 & 24 DLQI improvement at weeks 12 & 24 Adverse Events
References	Tessa B. Mullins, Poonam Sharma, Christopher A. Riley, Sidharth Sonthalia. Prurigo Nodularis. StatPearls [Internet]. Treasure Island (FL): StatPearls Publishing; 2021 Jan. 2020 Sep 15.  Eric H Kowalski, Diana Kneiber, Manuel Valdebran, Umangi Patel, Kyle T Amber. Treatment-resistant prurigo nodularis: challenges and solutions. Clin Cosmet Investig Dermatol. 2019 Feb 28;12:163-172. doi: 10.2147/CCID.S188070. eCollection 2019.

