### **5.4 Subject Enrollment and Treatment Assignment**

25 adult subjects of either gender with moderate-to-severe prurigo nodularis will receive upadacitinib 15mg once daily. Dosage will be increased to 30mg QD at week 8 based on subject response. See dosage adjustments below. IP will be managed by site personnel and stored in a temperature controlled limited access area at the study site. Accountability records will be maintained by site personnel for all IP receipt, dispensation and returns.

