### Contraception Requirements for Females

A female who is permanently surgically sterile or postmenopausal is not considered to be a female of childbearing potential and is not required to follow contraception recommendations.

Surgically sterile is defined as:

- bilateral oophorectomy (surgical removal of both ovaries); or
- bilateral salpingectomy (surgical removal of both fallopian tubes); or
- hysterectomy ( surgical removal of uterus)

Postmenopausal is defined as:

- Age  $\geq$  55 years with no menses for 12 or more months without an alternative medical cause; or.
- Age  $<$  55 years with no menses for 12 or more months without an alternative medical cause AND a follicle-stimulating hormone (FSH) level  $>$  40 IU/L.

If the female subject is  $\leq$  55 years of age, postmenarchal, and has had no menses for  $\geq$  12 months AND has no history of permanent surgical sterilization (defined above), FSH should be tested at Screening.

- If FSH is not tested, it is assumed that the subject is of childbearing potential and protocol specified contraception is required.
- If the FSH is tested and the result is consistent with postmenopausal status, contraception is not required.
- If the FSH is tested and the result is consistent with premenopausal status, contraception is required, and pregnancy testing requirements for women of childbearing potential must be followed (see below).

A female who does not meet the definition of postmenopausal or permanently surgically sterile is considered of childbearing potential and is required to practice at least one of the following highly effective methods of birth control that is effective from Baseline Visit (or earlier) through at least 30 days after the last dose of study drug.

- Combined (estrogen and progestogen containing) hormonal contraception (oral, intravaginal, transdermal) associated with the inhibition of ovulation, initiated at least 30 days prior to Baseline Visit.
- Progestogen-only hormonal contraception (oral, injectable, implantable) associated with inhibition of ovulation, initiated at least 30 days prior to Baseline Visit.
- Bilateral tubal occlusion/ligation.
- Vasectomized partner(s) provided the vasectomized partner has received medical confirmation of the surgical success and is the sole sexual partner of the women of childbearing potential trial participant.

- Intrauterine device.
- Intrauterine hormone-releasing system.

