## Appendix B

### WI-NRS

1. Numerical Rating Scale. On a scale from 0 (no itch) to 10 (worst imaginable itch)...

...how was your itch, on average, within the past 24 hours? Please select one number.

0    1    2    3    4    5    6    7    8    9    10

...how was your worst itch in the past 24 hours? Please select one number.

0    1    2    3    4    5    6    7    8    9    10

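### As written, the Week 8 dose rule in Section 5.5.1.3 is inverted: itch reductions of 3 or more points go to 30 mg, and reductions of 1 or 2 points stay on 15 mg

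*Combined protocol and SAP*

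**What the plan says.** All subjects start on 15 mg once daily. Section 5.5.1.3 then gives the Week 8 rule: "For subjects who do not achieve $\leq$ 2-point reduction in itch at week 8, upadacitinib dosage will be increased to 30mg QD". Its next sentence is the only provision for coming back down: "The investigator may reduce the dose to 15mg QD after week 16 per investigator discretion". The same section also stops the drug for a related adverse event that symptomatic treatment does not relieve.

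Section 5.4 mentions the increase but adds no threshold or direction: "Dosage will be increased to 30mg QD at week 8 based on subject response. See dosage adjustments below". Section 5.6 gives only the 15 mg to 30 mg range, and the synopsis has no dose rule. Section 5.5.1.3 is therefore the only operative statement.

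The endpoint fixes the direction of benefit. The synopsis defines the primary endpoint as "Proportion of participants with improvement (reduction) in worst-itch numeric rating scale (WI-NRS) by $\geq 4$ from baseline to Week 12", so a larger reduction is a better response.

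**The concern.** The sentence combines a negation with a less-than-or-equal sign, and together they turn the rule round. A subject whose itch fell by 1 or 2 points has achieved a reduction of at most 2 and stays on 15 mg. A subject whose itch fell by 3 or more has not, and goes to 30 mg.

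Two consequences follow, depending on what the site does:

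- **Followed literally**, clear improvers get double the daily dose from Week 8 and subjects with little improvement get no increase. This happens before the primary endpoint is measured, so it determines which dose that result reflects. The safety section lists serious infections, malignancy, major cardiovascular events and thrombotic events as events of special interest, and the plan gives no reason to raise exposure in subjects who already respond.
- **Followed as probably meant**, dosing departs from the written protocol. Section 8.2.1 allows a per-protocol population that leaves out major violators, and under Section 8.1 the investigator monitors the study's own records for compliance. The written rule is the standard for both.

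The sentence also refers only to itch. Appendix B has two itch items, "how was your itch, on average, within the past 24 hours" and "how was your worst itch in the past 24 hours", and these could give one subject two different doses.

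**Working it through.** The plan gives no figure to reproduce here. The check is one of logic, followed by simple dose arithmetic.

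**Inputs**
- Rule: increase if NOT (reduction ≤ 2), from Section 5.5.1.3.
- Scale: whole numbers 0 to 10, from Appendix B. A reduction above 2 is therefore 3 or more.
- Response criterion: reduction ≥ 4, from the synopsis.
- Doses: 15 mg daily from baseline, 30 mg daily if increased at Week 8.

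**Step 1. Dose assigned at Week 8.** Let r be the reduction from baseline, with r ≥ 1. Two corrections are plausible: increase if NOT (r ≥ 2), or increase if NOT (r > 2).

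| r | As written: NOT (r ≤ 2) | Corrected: NOT (r ≥ 2) | Corrected: NOT (r > 2) |
|---|---|---|---|
| 1 | 15 mg | 30 mg | 30 mg |
| 2 | 15 mg | 15 mg | 30 mg |
| 3 | 30 mg | 15 mg | 15 mg |
| 4 to 10 | 30 mg | 15 mg | 15 mg |

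The written rule gives the opposite dose from both corrections at r = 1 and at r ≥ 3. At r = 2 the answer depends on which correction the sponsor intends.

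No change or worsening (r ≤ 0) is left out because the written words are ambiguous there. Read as a number, 0 ≤ 2 holds and the subject stays on 15 mg. Read in ordinary language, no reduction was achieved and the subject goes to 30 mg.

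**Step 2. Example.** WI-NRS 8 at baseline and 4 at Week 8: r = 8 − 4 = 4, already a responder, goes to 30 mg. WI-NRS 8 and then 7: r = 8 − 7 = 1, stays on 15 mg. Either correction reverses both assignments.

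**Step 3. Cumulative dose for one subject escalated at Week 8**, with full adherence and the increase on day 56:
- To Week 12 (day 84): 15 × 56 + 30 × 28 = 840 + 840 = 1,680 mg, against 15 × 84 = 1,260 mg. Ratio 1,680 / 1,260 = 1.33.
- To Week 16 (day 112), after which a dose reduction is mentioned: 15 × 56 + 30 × 56 = 840 + 1,680 = 2,520 mg, against 15 × 112 = 1,680 mg. Ratio 2,520 / 1,680 = 1.50.

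**Step 4. Could the symbol be a misreading of the PDF?** The contraception text shows both symbols, correctly distinguished, within one sentence: "If the female subject is $\leq$ 55 years of age, postmenarchal, and has had no menses for $\geq$ 12 months". The endpoint definitions also show ≥ correctly. A misread is unlikely, though this does not prove that the symbol in Section 5.5.1.3 was read correctly.

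**The case against.** The strongest reply is that nobody would follow the sentence literally. Section 5.4 ties the increase to response, the phrasing is that of an adequacy threshold, and site staff would probably escalate poor responders. The harm is also bounded: 30 mg is a planned dose, a related adverse event can still lead to discontinuation, an earlier dose reduction is not forbidden, and this is an exploratory, single-centre, open-label study of 25 subjects with no hypothesis test specified.

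Much of this is fair. A mismatch between text and practice is the likelier outcome, and literal escalation of responders the less likely one. But intent does not complete the rule: accepting it still leaves a subject with exactly 2 points on 15 mg under one reading and 30 mg under the other.

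Three narrower points stand as limits:
- Only r = 1 and r ≥ 3 are inverted under both corrections. Keeping a 2-point subject on 15 mg may be what the sponsor wants. At 3 points, still below the response criterion, there could be an efficacy reason to increase. The clear reversal is between 4 or more points and 1 point.
- The milligram totals describe any subject escalated at Week 8, rightly or wrongly. The error changes who is escalated. Whether total exposure in the study rises or falls depends on the Week 8 responses, which the documents do not give.
- The choice of itch item is secondary. Section 5.6.7.1 defines only worst itch and the itch endpoints use only the WI-NRS, so the intended item is reasonably clear.

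**Conclusion.** The rule is wrong as written and needs correcting. It is mandatory, it is the only statement of the threshold, and it acts before the primary endpoint, whether that is taken as Week 12 (synopsis) or Week 16 (which Section 8.2 also names). Literally applied, it sends subjects who already meet the 4-point criterion to 30 mg and keeps those with a 1-point reduction on 15 mg.

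The size can be given per subject only: a doubled daily dose from Week 8, and 33% more drug by Week 12 or 50% more by Week 16, assuming full adherence and an increase exactly at Week 8. The number of subjects affected and the effect on the primary proportion are not estimated.

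The logical reading needs only the whole-number scale and the sentence as printed. That the symbol is a slip for ≥ is an inference, though a strong one. Confidence is high, with the small reservation that a misread symbol cannot be fully excluded.

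**What to change.** Replace the sentence in Section 5.5.1.3 with: *Subjects who do not achieve a ≥ 2-point reduction from baseline in WI-NRS (worst itch) at Week 8 will be increased to 30 mg QD.* The sponsor should confirm whether exactly 2 points is an adequate response. If it is not, use > 2 in place of ≥ 2. Either wording also settles no change and worsening, since both then go to 30 mg.

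The cost is a one-sentence amendment. Section 5.4 only cross-refers and needs no edit. The schedule of events in Section 8.3 already has questionnaires at Baseline and Week 8, so visits, data collection and analyses do not change.

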#### **5.5.3 Permitted Concomitant Therapy and Rescue Therapy**

Starting from the screening visit, subjects will be instructed to use a daily non-medicated moisturizer through the end of study participation. Appropriate interventions (e.g., prescribed medications) may be performed as the investigator deems necessary to treat concomitant illnesses and/or safeguard the subjects' wellbeing. No investigational product or device may be used during the study

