#### **5.6.4 Laboratory Testing**

Serum chemistry, hematology, Hepatitis B Surface Antibody and Antigen (HBV), Hepatitis C Antibody (HCV) and Quantiferon Gold testing will be performed at screening to ensure subject safety prior to baseline. Serum chemistry and hematology will also be performed at weeks 12 and 24.

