## **6 COMPLAINTS/ADVERSE EVENTS/SERIOUS ADVERSE EVENTS**

Adverse events will be collected from the time of the first dose of product during the study until 30 days following the intake of the last dose taken during the study period. An AE is defined as any untoward medical occurrence in a subject or clinical investigation subject administered a pharmaceutical product and which does not necessarily have a causal relationship with this treatment. An AE can therefore be any unfavorable and unintended sign (including an abnormal laboratory finding), symptom, or disease temporally associated with the use of a medicinal (investigational) product, whether or not the event is considered causally related to the use of the product.

Such an event can result from use of the drug as stipulated in the protocol or labeling, as well as from accidental or intentional overdose, drug abuse, or drug withdrawal. Any worsening of a pre-existing condition or illness is considered an AE. Worsening in severity of a reported AE should be reported as a new AE. Laboratory abnormalities and changes in vital signs are considered to be AEs only if they result in discontinuation from the study, necessitate therapeutic medical intervention, meets protocol specific criteria and/or if the investigator considers them to be AEs.

The investigator will monitor each subject for clinical and laboratory evidence of AEs on a routine basis throughout the study. All AEs will be followed to a satisfactory conclusion. An elective surgery/procedure scheduled to occur during a study will not be considered an AE if the surgery/procedure is being performed for a pre-existing condition and the surgery/procedure has been preplanned prior to study entry. Elective surgery will not be allowed during the study until the primary endpoint has been assessed (Week 16). However, if the pre-existing condition deteriorates unexpectedly during the study (e.g., surgery performed earlier than planned), then the deterioration of the condition for which the elective surgery/procedure is being done will be considered an AE. If any of the following events are reported, then the following supplemental form must be completed. If an AE meets any of the following criteria, it is to be reported to AbbVie as an SAE within 24 hours of the site being made aware of the SAE:

Death of Subject- An event that results in the death of a subject.

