### Adverse Events of Special Interest

The following AESIs will be monitored during the study:

- Serious infections
- Opportunistic infections
- Herpes zoster
- Tuberculosis
- Malignancy (all types)
- GI perforations
- Adjudicated cardiovascular events (e.g., major adverse cardiovascular event [MACE])
- Anemia
- Neutropenia
- Lymphopenia
- Increased serum creatinine and renal dysfunction
- Hepatic events and increased hepatic transaminases
- Elevated creatine phosphokinase
- embolic and thrombotic events (non-cardiac, non-central nervous system)

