### Adverse Event Severity and Relationship to Study Drug

The investigators will rate the severity of each AE according to the National Cancer Institute Common

Terminology Criteria for Adverse Events version 4.03.

If no grading criteria are provided for the reported event, then the event should be graded follows:

Mild (Grade 1) Asymptomatic or mild symptoms; clinical or diagnostic observations only; intervention not indicated

Moderate (Grade 2) Minimal, local or noninvasive intervention indicated; limiting age-appropriate instrumental activities of daily living (ADL)

Severe (Grade 3 to 5) Grade 3 Severe or medically significant but not immediately life-threatening; hospitalization or prolongation of hospitalization indicated; disabling; limiting self-care ADL (selfcare ADL refer to bathing, dressing and undressing, feeding self, using the toilet, taking medications, and not bedridden)

Grade 4 Life-threatening consequences; urgent intervention indicated

Grade 5 Death related to AE

The investigator will use the following definitions to assess the relationship of the AE to the use of study drug:

Reasonable Possibility – After consideration of factors including timing of the event, biologic plausibility, clinical judgment, and potential alternative causes, there is sufficient evidence (information) to suggest a causal relationship.

No Reasonable Possibility – After consideration of factors including timing of the event, biologic plausibility, clinical judgment, and potential alternative causes, there is insufficient evidence (information) to suggest a causal relationship. For causality assessments, events assessed as having a reasonable possibility of being related to the study drug will be considered "associated." Events assessed as having no reasonable possibility of being related to study drug will be considered "not associated." In addition, when the investigator has not reported a causality or deemed it not assessable, AbbVie will consider the event associated.

If an investigator's opinion of no reasonable possibility of being related to study drug is given, an Other cause of event must be provided by the investigator for the SAE.

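### The stopping rule for non-serious related events does not fit symptom-free laboratory AESIs; no action level, repeat test or hold is set, and the first on-treatment labs are dated two ways

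*Combined protocol and SAP*

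**What the plan says.** Section 5.5.1.3 (Upadacitinib Dosage Adjustments) applies to SAEs and, for other events, sets this condition: "an adverse event that is thought to be related to study drug and is not alleviated by symptomatic intervention, study drug will be discontinued". The only dose reduction in the plan is in the same section: "The investigator may reduce the dose to 15mg QD after week 16 per investigator discretion".

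Section 6 lists 14 adverse events of special interest. Six depend wholly or partly on blood results: anemia, neutropenia, lymphopenia, creatinine and renal dysfunction, CPK, and "Hepatic events and increased hepatic transaminases". On when a laboratory change becomes an AE, Section 6 says "Laboratory abnormalities and changes in vital signs are considered to be AEs only if they result in discontinuation from the study", need therapeutic intervention, or if the change "meets protocol specific criteria and/or if the investigator considers them to be AEs". Severity is rated by CTCAE v4.03. For events that CTCAE does not cover, Grade 3 is described as "Severe or medically significant but not immediately life-threatening". No grade is tied to an action.

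On timing, Section 5.6.4 says "Serum chemistry and hematology will also be performed at weeks 12 and 24". The safety-labs row of the Schedule of Events (Section 8.3) marks screening, Week 16 and Week 24.

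**The concern.** For a non-serious related event, the stated test is whether treating the symptoms helps. A raised transaminase or CPK, or a low neutrophil count, often has no symptom to treat, so the test gives no usable answer for events that the protocol itself names as special risks. A reader who looks elsewhere for a level finds a pointer to protocol-specific criteria and no criteria.

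This matters because the dose may double at Week 8 and scheduled on-treatment blood tests are few. Without a written level, two similar results can be handled differently, and nobody can later check whether the protocol was followed. The investigator self-monitors the records (Section 8.1), so a written level would be the main check. Stopping also bears on the data. The efficacy section uses assessments made before premature discontinuation of drug and imputes nothing, so a stop after the first on-treatment draw would, on the natural reading, remove that subject from the Week 24 results.

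**Working it through.** The plan gives no figure to reproduce. The check sets the provisions side by side and then does the timing arithmetic.

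**Step 1. Which provisions could stop or change drug for a laboratory event?**

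| Provision | What triggers it | Level set? | Hold or repeat test? |
|---|---|---|---|
| 5.5.1.3, SAE limb | An SAE (the clause lacks a verb; read here as any SAE) | The SAE definitions only | None |
| 5.5.1.3, related-AE limb | No relief from treating symptoms | None | None |
| 5.5.1.3, dose reduction | Discretion, after Week 16 | None | Not a hold |
| 6, important medical event | Medical judgment; blood dyscrasias without admission are an example | None | None |
| 5.6.8 item 2 | An AE that, among other things, raises the subject's risk | None | Ends participation |
| 5.5.3 | Interventions that "may be performed as the investigator deems necessary to treat concomitant illnesses" or protect wellbeing | None | Not mentioned |
| 5.2.2, exclusion 18 | Investigator's opinion, at entry only | None | Not applicable |

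The only numeric laboratory limit in the document is FSH > 40 IU/L, which defines menopausal status. The protocol-specific criteria are mentioned once, in Section 6, and are set out in no section or appendix.

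**Step 2. How many listed events are affected?** Laboratory-based AESIs: 6. Listed AESIs: 14. 6/14 = 42.9%. Of the 6, those with a stated action level: 0. This counts list entries and does not measure risk.

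**Step 3. When does the first scheduled result arrive?** Treatment lasts 24 weeks and the increase to 30 mg is at Week 8.

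| | 5.6.4 | 8.3 |
|---|---|---|
| On-treatment draws | Weeks 12, 24 | Weeks 16, 24 |
| Draws before treatment ends | 1 of 2 | 1 of 2 |
| Time on drug before the first draw | 12/24 = 50% | 16/24 = 67% |
| Time at 30 mg before the first draw | 12 − 8 = 4 weeks | 16 − 8 = 8 weeks |
| Gap from first draw to Week 16 | 16 − 12 = 4 weeks | 0 weeks |

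Under either timing, one scheduled draw can alter dosing. Under the Week 12 timing, its result comes 4 weeks before the point after which the plan provides for a reduction to 15 mg.

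**The case against.** The strongest reply is that the investigator already has the means to act. Section 5.6.8 item 2 is mandatory: a subject whose AE raises risk is withdrawn. Section 6 gives blood dyscrasias as an example of an important medical event, so a serious anemia, neutropenia or lymphopenia can reach the SAE limb. Section 6 also requires routine monitoring for laboratory evidence of AEs, which leaves room for unscheduled tests. In a single-center study of 25 subjects, judgment may be thought enough.

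This reply stands in part, and it rules out several stronger readings that a reader might infer:

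- **That the stopping rules cannot be applied to laboratory events at all.** They can, through the two routes above. Those routes set no level, and Section 5.6.8 ends participation rather than pausing drug.
- **That the definitions are circular,** because an abnormality is an AE if it leads to discontinuation and discontinuation needs an AE. Section 6 speaks of leaving the study, which has routes that need no AE, and it separately lets the investigator declare an AE.
- **That the rule ranges from a forced stop at Grade 1 to no stop at Grade 3.** That takes one sentence in isolation. A trivial change is an AE essentially only if the investigator calls it one, and a Grade 3 change that raises risk falls under Section 5.6.8.
- **That a subject on 30 mg with an abnormal result must stay on 30 mg or stop.** At most this describes the Week 12 timing. With a Week 16 draw, the discretionary reduction is about to open. The plan is also silent on interruption, which is not a ban: Section 5.5.1.3 refers to subjects who stop permanently.

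What remains is that judgment is the only guide, although Section 6 refers to criteria as if they existed.

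**Conclusion.** The concern holds in a limited form. The symptom-relief test in Section 5.5.1.3 does not fit six of the 14 listed AESIs when they occur without symptoms. For those six, the plan gives no preset level, repeat test or temporary hold, and the criteria cited in Section 6 are undefined. Separately, Sections 5.6.4 and 8.3 contradict each other on the first on-treatment labs, by 4 weeks.

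This rests on three assumptions: that any SAE stops drug, which is the natural reading of an incomplete sentence; that the chemistry panel, whose contents are not listed, includes creatinine, transaminases and CPK; and that Week 24 ends dosing. The documents give no rate of laboratory events, so neither a number of subjects nor an effect on the efficacy results can be stated. The sponsor should correct this. It does not invalidate the design.

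**What to change.** 1. Add to Section 5.5.1.3:

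> For a laboratory AESI in Section 6 that is not an SAE, study drug will be interrupted at CTCAE v4.03 Grade 3 or higher (or a stricter level set by the sponsor) and the test repeated. Study drug will be permanently discontinued if the repeat remains at or above that level. Laboratory events that meet an SAE criterion follow the SAE rule. Section 5.6.8 item 2 continues to apply to lower-grade events that increase risk. These are the protocol specific criteria referred to in Section 6.

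   Grade 3 is a proposed default on the scale already in use. The sponsor may choose stricter levels, provided each of the six events has one. The last three sentences keep each event under one rule and leave the judgment route open.

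2. Allow reduction from 30 mg to 15 mg for safety at any time after the increase, not only after Week 16.

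3. Give the same week for the first on-treatment labs in Sections 5.6.4 and 8.3. Week 12 is preferable: it is an existing visit and the earlier check after the Week 8 increase.

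4. Complete the sentence on SAEs in Section 5.5.1.3, stating whether any SAE or only a related one stops drug.

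The cost is a short amendment, occasional repeat blood tests and brief dose interruptions in subjects who reach a threshold. No visit or subject is added.
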